## **8.8 Electrocardiograms**

Electrocardiograms (ECGs) will be performed in triplicate and sent to a central reviewer. Subjects should be lying quietly in a fully supine position for at least 10 minutes prior to each 12-lead ECG. A 12-lead ECG will be performed at the Screening Visit, Study Day 1, Week 2, Week 6, Week 10, Week 12, and the ET Visit, if applicable.

The Investigator will assess ECG data as normal, abnormal not clinically significant, or abnormal clinically significant. Any clinically significant abnormalities should be documented as medical history/adverse event/SAE as applicable. All ECG traces will be kept as source data.

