### 9.3.2 Analysis of Safety

Safety will be assessed using the SAS. The assessment of safety will include adverse events, clinical laboratory assessments, ECGs, physical examinations, and vital signs. In addition, the safety assessment will be based primarily on the frequency of new or worsening adverse events, laboratory abnormalities, and serious adverse events (SAEs). Other safety data will be summarized as appropriate.

AEs will be coded using the most recent version of the Medical Dictionary for Regulatory Activities (MedDRA). The summarization of AEs will include only treatment-emergent AEs (TEAEs), defined as AEs that begin or worsen after randomization and ingestion of the first dose of study drug. TEAEs and SAEs will be summarized by system organ class (SOC), severity, and relationship to study drug for each treatment group. Deaths, withdrawal from study treatment due to AEs, and withdrawal from the study due to AEs will each be summarized by treatment group.

Safety laboratory data will be summarized by treatment group at baseline, and at each post-baseline time point, if applicable, and change from baseline to End of Treatment (Week 12) or the ET Visit, if applicable. Baseline for safety laboratory data will be defined as the last pre-dose value (pre-dose Study Day 1/Visit T1 or prior). Frequency counts of new or worsening abnormalities will also be provided.

Vital signs data (value and change from baseline, where appropriate) will be summarized by treatment group at baseline and at each post-baseline time point. Baseline for vital signs data will be defined as the last pre-dose value (pre-dose Study Day 1/Visit T1 or prior). Abnormalities in ECGs and in PEs will be summarized.

All safety data will be listed.

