### 12.1 Adverse Events

AEs will be coded using Medical Dictionary for Regulatory Activities (MedDRA) version 19.1. All AE tables will be summarized for overall by treatment group and by stable statin use at baseline (according to the CRF) within treatment group. Except for the AE overview table and summaries of serious adverse events (SAEs) and AEs resulting in death (both of which will include all AEs), AE tables will only include summaries of treatment-emergent adverse events (TEAEs). A TEAE is defined as an AE with start date on or after the first dose date and less than 30 days after the last dose date. If AE start date is missing, the AE is assumed to be a TEAE. An AE overview table containing the frequency and percent of the following will be summarized by treatment group, and treatment group within each baseline statin (yes or no):

- Number of subjects with at least one TEAE, drug-related TEAE, SAE, drug-related SAE;
- Number of subjects who discontinued study treatment due to TEAE, drug-related TEAE, SAE, and drug-related SAE;
- Number of subjects who discontinued the study due to a TEAE; and
- Number of subjects who had a study treatment interruption due to a TEAE;
- Number of deaths and deaths due to a drug-related TEAE.

Additionally, the following will be summarized by treatment group, and treatment group within each stratum:

- TEAEs by system organ class (SOC) and preferred term (PT);
- TEAEs by descending PT ;
- TEAEs by SOC, PT, and maximum severity;
- Related TEAEs by SOC and PT;

- Related TEAEs by descending PT;
- SAEs by SOC and PT;
- Related SAEs by SOC and PT;
- TEAEs leading to treatment discontinuation by SOC and PT;
- Related TEAEs leading to treatment discontinuation by SOC and PT; and
- AEs that resulted in death by SOC and PT.

Summaries of SOC and PT will be sorted alphabetically by SOC and by decreasing frequency of PT in the total column for the gemcabene 600 mg group, followed by the 300 mg group, then placebo.

Note that the overview of AEs will be provided separately for the double-blind treatment period and follow-up period, to allow for a delivery of the double-blind data only during the database freeze.

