### 12.3 ECGs

ECGs will be performed in triplicate at the Screening Visit, Day 1, Week 2, Week 6, Week 10, Week 12, and the ET Visit, if applicable. The following ECG parameters will be reported by the central reader: heart rate, PR interval, QRS duration, QT interval (uncorrected), QT interval corrected for heart rate using QT interval corrected for heart rate with Bazett's formula (QTcB) and using QT interval corrected for heart rate with Fridericia's formula (QTcF), and T-wave amplitude. The average of the non-missing values for a given ECG parameter (eg, heart rate) will be used for analysis. In cases where only one ECG is performed, the result of the single ECG will be used. CFBL will be calculated for each parameter at each time point (including end of treatment) and summarized by treatment group.

Further, QTcB and QTcF will also be investigated through PCS criteria (see Table 4). The number and percent of subjects meeting the criteria below will be summarized by treatment group using the SAS. Summaries will be given for both overall (ie, any time post-baseline) and by visit. Subjects will be included in all categories for which they qualify. For criteria on the "Actual" values, the denominator for the percentages is the number of subjects who had a post-baseline assessment for each parameter. For criteria on the change, the denominator is the number of subjects who had a baseline and post-baseline assessment.

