**Table 4. ECG PCS Criteria**

ECG Parameter	Actual or Change	PCS Criteria
QTcB (msec)	Actual	> 450
	Actual	> 480
	Actual	> 500
	CFBL (increase)	> 30
	CFBL (increase)	> 60
	Actual	> 450
QTcF (msec)	Actual	> 480
	Actual	> 500
	CFBL (increase)	> 30
	CFBL (increase)	> 60

CFBL = change from baseline, ECG = electrocardiogram, PCS = potentially clinically significant, QTcB = QT interval corrected for heart rate with Bazett's formula, QTcF = QT interval corrected for heart rate with Fridericia's formula.

All interpretations along with the corresponding details will be provided in a listing.

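### The protocol promises a summary of ECG abnormalities, but the SAP only lists the ECG interpretations, so no table counts by arm the subjects whose ECG became abnormal or worsened.

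*Protocol*

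**What the plan says.** Protocol 9.3.2, with the same sentence in the synopsis, commits to this: "Abnormalities in ECGs and in PEs will be summarized". A separate sentence then says that all safety data will be listed, so the protocol treats summarizing and listing as two different things. ECG results are a named secondary safety endpoint (Protocol 2.2.4, SAP 6.2.2).

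Protocol 8.8 defines the graded reading: "The Investigator will assess ECG data as normal, abnormal not clinically significant, or abnormal clinically significant". It also sends the top grade onward: "Any clinically significant abnormalities should be documented as medical history/adverse event/SAE as applicable".

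SAP 12.3 handles the centrally read measurements by arm: "CFBL will be calculated for each parameter at each time point (including end of treatment) and summarized by treatment group". It adds by-arm counts of subjects crossing the QTcB and QTcF thresholds in Table 4. On the graded readings it has one sentence: "All interpretations along with the corresponding details will be provided in a listing".

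SAP 4.3 lists the changes from the protocol analyses. None concerns ECGs.

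**The concern.** A change-from-baseline summary of PR or QRS describes the group. It does not say how many subjects moved from a normal to an abnormal tracing, and a few such subjects can leave the mean and median almost unchanged. Rhythm findings, and morphology other than T-wave amplitude, have no measured parameter in SAP 12.3 at all. The investigator's grade is the only ECG field that covers every type of abnormality, and it is the field with no table.

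At stake is whether the report can state, for each arm and by a rule fixed in advance, how many subjects had a new or worsened ECG interpretation. The shift matters more than the raw count because some subjects may enter with an abnormal ECG. Eligibility allows stable angina, heart failure below NYHA Class III, and major cardiovascular events more than 3 months before screening. Without a baseline comparison, new and pre-existing findings cannot be separated.

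**Working it through.** The plan gives no figure on this point, so the check is a comparison of text plus one count.

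**Step 1. Where each kind of ECG information goes.**

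| Information | Source | By-arm output in the SAP |
|---|---|---|
| Heart rate, PR, QRS, QT, QTcB, QTcF, T-wave amplitude | Central reader, SAP 12.3 | Change from baseline at each time point |
| QTcB and QTcF above 450, 480, 500 msec; increases above 30 and 60 msec | SAP Table 4 | Number and percent, any time post-baseline and by visit |
| Abnormality graded clinically significant and reported as an adverse event | Protocol 8.8, SAP 12.1 | Treatment-emergent events by organ class and preferred term |
| Abnormality graded not clinically significant | Protocol 8.8 | None; listing only |
| Change in overall grade from baseline | Protocol 8.8 | None; listing only |

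The last two rows are the gap. The adverse event tables do not close it. They take only the top grade, and they give counts by preferred term rather than the number of subjects whose ECG interpretation worsened.

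**Step 2. How the SAP treats comparable safety data.** The protocol sentence covers ECGs and physical examinations together. SAP 12.5 carries out the physical-examination part by counting normal and abnormal findings, with percentages, by actual treatment group and visit. SAP 12.2 gives laboratory parameters a low/normal/high shift from baseline to end of treatment. Graded ECG interpretations get neither treatment, and SAP 4.3 gives no reason.

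**Step 3. How many assessments are involved.** Inputs: 90 randomized subjects (Protocol 9.1) and post-baseline ECGs at Weeks 2, 6, 10 and 12 (Protocol 8.8).

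- Scheduled assessments = subjects x visits = 90 x 4 = 360.
- If the planned 15% dropout all occurred before Week 2: 360 x 0.85 = 306.

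So between 306 and 360 scheduled assessments are affected, not counting early-termination visits. This assumes one grade per subject per visit. The protocol takes ECGs in triplicate and does not say whether each tracing is graded separately. The measurements from these same ECGs do enter the by-arm tables; only the interpretation field does not.

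The documents give no background rate of abnormal ECGs, so the number of subjects who would show a shift cannot be estimated.

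**The case against.** The strongest reply is that the protocol sentence is loose. It names no grade, no shift and no by-arm format, while the neighbouring sentences on laboratory data and vital signs do specify summaries by treatment group. A by-arm count of QTc outliers is a summary of one kind of ECG abnormality, so the SAP authors could reasonably have thought the commitment met. This stands in part: the SAP narrows the promise and does not abandon it. It does not explain why the other half of the same sentence became normal/abnormal counts.

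A reader might infer that new rhythm, conduction or repolarization abnormalities are not compared between arms at all. The documents do not support that. PR and QRS (conduction), and QT, QTcB, QTcF and T-wave amplitude (repolarization), are summarized by arm as change from baseline. QTc outliers are counted by arm, and clinically significant findings of any type can reach the adverse event tables.

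A reader might also infer that information is lost. It is not. Every interpretation is listed, and counts could be made by hand once treatment is known. What is lost is a rule fixed in advance for baseline, worst value and denominator.

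Finally, the yield may be small. Uncontrolled arrhythmia and prolonged QTcF are exclusions, Protocol 1.4 reports no clinically relevant QTc effect so far, and Protocol 9.3.2 rests safety primarily on adverse events, laboratory abnormalities and serious adverse events. That argues for low severity, not for leaving the gap.

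**Conclusion.** The point holds in a limited form and is minor. The SAP would not produce a by-arm count of subjects with a new or worsened ECG interpretation, although the protocol says ECG abnormalities will be summarized, and the SAP does not declare the difference. The gap lies mainly in findings graded not clinically significant, and in rhythm or morphology findings outside the measured parameters. No efficacy conclusion depends on it. Safety analysis is descriptive only (SAP 12), so the table would support no formal test.

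The conclusion rests on two assumptions: that the interpretations mentioned in SAP 12.3 are the grades defined in Protocol 8.8, and that no such table is planned elsewhere. SAP 12.3 shows no redaction in the text supplied.

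**What to change.** Add to SAP 12.3 one descriptive table by actual treatment group on the Safety Analysis Set:

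- the shift in interpretation across the three grades, from baseline to the worst post-baseline grade and from baseline to end of treatment;
- the number and percent of subjects with a new or worsened interpretation, with subjects having both a baseline and a post-baseline interpretation as the denominator.

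Use the existing ECG baseline (SAP 9.3), the safety definition of end of treatment (SAP 9.2) and the 5-day limit after last dose (SAP 9.8). State how a triplicate yields one grade, because the averaging rule in SAP 12.3 suits measurements but not grades. Keep the listing. Settle this before treatment codes are requested under SAP 4.1. If the sponsor prefers no table, SAP 4.3 should record the narrowing and the reason.

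The cost is a few lines of SAP text and one extra table, with no new data. The drawback is that sites may differ in what they grade as not clinically significant. Site staff are blinded (Protocol 5.3), so this should add noise rather than favour an arm.

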## **10 DATA MANAGEMENT AND RECORD KEEPING**

### **10.1 Data Management**

#### **10.1.1 Data Handling**

Data will be recorded at the site on eCRFs and reviewed by the CRA during monitoring visits. The CRAs will verify data recorded in the EDC system with source documents. All corrections or changes made to any study data must be appropriately tracked in an audit trail in the EDC system. An eCRF will be considered complete when all missing, incorrect, and/or inconsistent data has been accounted for.

#### **10.1.2 Computer Systems**

Data will be collected and processed using a validated EDC system. The system and procedures are designed in compliance with Title 21 of the Code of Federal Regulations (21 CFR Part 11).

#### **10.1.3 Data Entry**

Data must be recorded using the EDC system as the study is in progress. All site personnel must log into the system using their secure user name and password in order to enter, review, or correct study data. These procedures must comply with 21 CFR Part 11 and other appropriate international regulations. All passwords will be strictly confidential.

#### **10.1.4 Medical Information Coding**

For medical information, the following thesauri will be used:

- Latest version of the Medical Dictionary for Regulatory Activities (MedDRA) for medical history and adverse events, and
- World Health Organization Drug (WHO Drug) Dictionary for prior and concomitant medications.

#### **10.1.5 Data Validation**

Validation checks programmed within the EDC system, as well as supplemental validation performed via review of the downloaded data, will be applied to the data in order to ensure accurate, consistent, and reliable data. Data identified as erroneous, or data that are missing, will be referred to the investigative site for resolution through data queries.

The eCRFs must be reviewed and electronically signed by the Investigator.

## **10.2 Record Keeping**

Records of subjects, source documents, monitoring visit logs, eCRFs, inventory of study product, regulatory documents, and other Sponsor correspondence pertaining to the study must be kept in the appropriate study files at the site. Source data is defined as all information in original records and certified copies of original records of clinical findings, observations, or other activities in a clinical study necessary for the evaluation and reconstruction of the clinical study. Source data are contained in source documents (original records or certified copies). These records will be retained in a secure file for the period as set forth in the Clinical Study Agreement. Prior to transfer or destruction of these records, the Sponsor must be notified in writing and be given the opportunity to further store such records.

## **11 INVESTIGATOR REQUIREMENTS AND QUALITY CONTROL**

### **11.1 Ethical Conduct of the Study**

Good Clinical Practice (GCP) is an international ethical and scientific quality standard for designing, conducting, recording, and reporting studies that involve human subjects. Compliance with this standard provides public assurance that the rights, safety, and well-being of study subjects are protected, consistent with the principles that have their origin in the Declaration of Helsinki, and that the clinical study data are credible.

### **11.2 Institutional Review Board/Ethics Committee**

Federal regulations and the International Conference on Harmonisation (ICH) require that approval be obtained from an Institutional Review Board (IRB)/Ethics Committee (EC) prior to participation of subjects in research studies. The IRB/EC will review all appropriate study documentation in order to safeguard the rights, safety, and well-being of subjects. The study will only be conducted at sites where IRB/EC approval has been obtained. The protocol, Investigator's Brochure, Informed Consent Form (ICF), advertisements (if applicable), written information given to the subjects, safety updates, annual progress reports, and any revisions to these documents will be provided to the IRB/EC by the Investigator.

Prior to study onset, the protocol, any protocol amendments, ICFs, advertisements to be used for subject recruitment, and any other written information regarding this study being provided to a subject or subject's legal guardian must be approved by the IRB/EC.

No drug will be released to the site for dosing until written IRB/EC authorization has been received by the Sponsor, or designee.

### **11.3 Informed Consent**

The ICF and any changes to the ICF made during the course of the study must be agreed to by the Sponsor or designee and the IRB/EC prior to its use and must be in compliance with all ICH GCP, local regulatory requirements, and legal requirements.

The Investigator, or a person delegated the responsibility by the Investigator, must ensure that each study subject (or legally acceptable representative) is fully informed about the nature and objectives of the study and possible risks associated with participation and must ensure that the subject has been informed of his/her rights to privacy. The Investigator or delegate will allow the subject adequate opportunity to read the written informed consent and ask any questions. The Investigator will obtain written informed consent from each subject before any study-specific activity is performed and should document in the source documentation that consent was obtained prior to any study-specific activity. The original signed copy of the ICF must be maintained by the Investigator and is subject to inspection by a representative of the Sponsor, their representatives, auditors, the IRB/EC and/or regulatory agencies. A copy of the signed ICF will be given to the subject.

#### **11.4 Study Monitoring Requirements**

It is the responsibility of the Investigator to ensure that the study is conducted in accordance with the protocol, ICH GCP, Directive 2001/20/EC, applicable regulatory requirements, and the Declaration of Helsinki (Seoul 2008) and that valid data are entered into the eCRFs.

The role of the study monitor is to verify the rights and well-being of the subjects are protected, the data is accurate, complete, and verifiable from source documents, and the conduct of the study is in compliance with the protocol, Declaration of Helsinki, ICH GCP, and applicable regulatory requirements.

To achieve this objective, the monitor's duties are to aid the Investigator and, at the same time, the Sponsor in the maintenance of complete, legible, well organized and easily retrievable data. Before the enrollment of any subject in this study, the Sponsor or their designee will review with the Investigator and site personnel the following documents: protocol, Investigator's Brochure, eCRFs and procedures for their completion, informed consent process, management of investigational product, and the procedure for reporting adverse events such as SAEs.

The Investigator will permit the Sponsor or their designee to monitor the study as frequently as deemed necessary to determine that data recording and protocol adherence are satisfactory. During the monitoring visits, information recorded on the eCRFs will be verified against source documents and requests for clarification or correction may be made. After the eCRF data is entered by the site, the CRA will review the data for safety information, completeness, accuracy, and logical consistency. Computer programs that identify data inconsistencies may be used to help monitor the clinical study. If necessary, requests for clarification or correction will be sent to Investigators. The Investigator and his/her staff will be expected to cooperate with the monitor and provide any missing information, whenever possible.

All monitoring activities will be reported and archived. In addition, monitoring visits will be documented at the investigational site by signature and date on the study-specific monitoring log and findings documented in a follow-up letter.

#### **11.5 Disclosure of Data**

Data generated by this study must be available for inspection by the FDA, the Sponsor or their designee, applicable foreign health authorities, and the IRB/EC as appropriate. Subjects or their legal representatives may request their medical information be given to their personal physician or other appropriate medical personnel responsible for their welfare.

Subject medical information obtained during the study is confidential and disclosure to third parties other than those noted above is prohibited.

#### **11.6 Retention of Records**

To enable evaluations and/or audits from regulatory authorities or the Sponsor, the Investigator will keep records, including the identity of all participating subjects (sufficient information to link records, e.g., eCRFs and hospital records), all original signed ICFs, copies of all eCRFs, SAE forms, source documents, and detailed records of treatment disposition. The records should be retained by the Investigator according to specifications in the ICH guidelines, local

regulations, or as specified in the Clinical Study Agreement, whichever is longer. **The Investigator must obtain written permission from Gemphire before disposing of any records, even if retention requirements have been met.**

If the Investigator relocates, retires, or for any reason withdraws from the study, the Sponsor should be prospectively notified. The study records must be transferred to an acceptable designee, such as another Investigator, another institution, or to the Sponsor.

